1.1. The EuroQol Group

- The EuroQol Group is a network of international multidisciplinary researchers devoted to the measurement of health status. Established in 1987, the EuroQol Group originally consisted of researchers from Europe, but nowadays includes members from North America, Asia, Africa, Australia, and New Zealand. The Group is responsible for the development of EQ-5D, a preference based measure of health status that is now widely used in clinical trials, observational studies and other health surveys.
- The EuroQol Group has been holding annual scientific meetings since its inception in 1987.
- The EuroQol Group can be justifiably proud of its collective scientific achievements over the last 20 years. Research areas include: valuation, EQ-5D use in clinical studies and in population surveys, experimentation with the EQ-5D descriptive system, computerized applications, interpretation of EQ-5D ratings and the role of EQ-5D in measuring social inequalities in self-reported health.
- The EuroQol Group's website (www.euroqol.org) contains detailed information about EQ-5D, guidance for users, a list of available language versions, EQ-5D references and contact details.

1.2. EQ-5D

EQ-5D is a standardised measure of health status developed by the EuroQol Group in order to provide a simple, generic measure of health for clinical and economic appraisal¹. Applicable to a wide range of health conditions and treatments, it provides a simple descriptive profile and a single index value for health status that can be used in the clinical and economic evaluation of health care as well as in population health surveys (Figure 1).

[figure not shown]
EQ-5D is designed for self-completion by respondents and is ideally suited for use in postal surveys, in clinics, and in face-to-face interviews. It is cognitively undemanding, taking only a few minutes to complete. Instructions to respondents are included in the questionnaire.

[figure not shown]
1.2.1. EQ-5D-3L

The EQ-5D 3 level version (EQ-5D-3L) was introduced in 1990. The EQ-5D-3L essentially consists of 2 pages - the EQ-5D descriptive system (page 2) and the EQ visual analogue scale (EQ VAS) (page 3). The EQ-5D-3L descriptive system comprises the following 5 dimensions: mobility, self-care, usual activities, pain/discomfort and anxiety/depression. Each dimension has 3 levels: no problems, some problems, extreme problems. The respondent is asked to indicate his/her health state by ticking (or placing a cross) in the box against the most appropriate statement in each of the 5 dimensions. The EQ VAS records the

¹ EuroQol Group. EuroQol-a new facility for the measurement of health-related quality of life. Health Policy 1990;16:199-208

respondent's self-rated health on a vertical, visual analogue scale where the endpoints are labelled 'Best imaginable health state' and 'Worst imaginable health state'. This information can be used as a quantitative measure of health outcome as judged by the individual respondents. **It should be noted that the numerals 1-3 have no arithmetic properties and should not be used as a cardinal score.**

[figure not shown]

Part 5: Minnesota Living with Heart Failure Questionnaire**Instructions for use:**

1. Patients should respond to the questionnaire prior to other assessments and interactions that may bias responses. You may tell the patient that you would like to get his or her opinion before performing other medical assessments.
2. Ample, uninterrupted time should be provided for the patient to complete the questionnaire.
3. The following instructions should be given to the patient each time the questionnaire is completed.
 - a. Read the introductory paragraph at the top of the questionnaire to the patient.
 - b. Read the first question to the patient - "Did your heart failure prevent you from living as you wanted during the last month by causing swelling, for example, in your ankles, legs"? Tell the patient, "If you did not have any ankle or leg swelling during the last month you should circle nought after this question to indicate that swelling was not a problem during the last month". Explain to the patient that if he or she did have swelling that was caused by a sprained ankle, or some other cause that was definitely not related to heart failure, he or she should also circle nought. Tell the patient, "If you are not sure why you had the swelling or think it was related to your heart condition, then rate how much the swelling prevented you from doing things you wanted to do and from feeling the way you would like to feel". In other words, how bothersome was the swelling? Show the patient how to use the 1 to 5 scale to indicate how much the swelling affected his or her life during the last month - from very little to very much.
4. Let the patient read and respond to the other questions. The entire questionnaire may be read directly to the patient, being careful not to influence responses by verbal or physical cues.
5. Check to make sure the patient has responded to each question and that there is only one answer clearly marked for each question. If a patient elects not to answer a specific question(s) indicate so on the questionnaire.
6. Score the questionnaire by adding the responses to all 21 questions. In addition, physical (items 2, 3, 4, 5, 6, 7, 12 and 13) and emotional (items 17, 18, 19, 20, and 21) dimensions of the questionnaire have been identified by factor analysis, and may be examined to further characterize the effect of heart failure on a patient's life.

These questions concern how your heart failure (heart condition) has prevented you from living as you wanted during the last month. The items listed below describe different ways some people are affected. If you are sure an item does not apply to you or is not related to your heart failure, then circle 0 (No) and go on to the next item. If an item does apply to you, then circle the number relating to how much it prevented you from living as you wanted.

Part 6: MultiPoint Pacing Vectors Test

This appendix describes the test procedure (Vector Test) that needs to be performed in order to establish if the MPP feature can be turned ON. The feature will be tested at the Classification visit.

1.0 INTRODUCTION

This document is a statistical analysis plan for the MORE-CRT MPP trial ([REDACTED]).

2.0 TRIAL OBJECTIVES

The objective of this clinical trial is to assess the impact of the MultiPoint Pacing (MPP) feature at 12 months in the treatment of patients that are not responding to standard Cardiac Resynchronization Therapy (CRT) after 6 months. Due to the many combinations of parameters available for MPP programming, the MPP feature will be evaluated in two scenarios:

- (1) without mandated MPP programming parameters, and
- (2) with mandated MPP programming parameters.

The primary objective is

- To demonstrate that the activation of the MPP feature will increase the rate of CRT responders in patients who are classified as non-responders at 6 months of follow-up.

The secondary objective is

- To assess the impact of the MPP feature on patients' functional and clinical status

3.0 TRIAL DESIGN

This study is designed as a prospective, randomized, multi-center trial. Data will be collected at Enrollment, Baseline, Implant Procedure, Patient Classification, and at 6-month and 12-month follow-up visits.

At the 6-month visit, the subject's response to CRT will be evaluated according to left ventricular end systolic volume (LVESV) reduction as follows:

Study Document No: [REDACTED]

Study Name: MORE CRT MPP

Statistical Analysis Plan

- Subjects with a LVESV reduction of at least 15% relative to baseline will be classified as responders: these subjects will terminate their participation in the study and return to the center's standard practice.
- Subjects with a LVESV reduction of less than 15% relative to baseline will be classified as non-responders: for these subjects, the MPP feature will be activated according to randomization result (MPP ON versus MPP OFF) and they will be followed until the 12-month visit.

In the **first phase** of the study (Phase I), for those subjects who are randomized to **MPP ON**, the MPP feature is programmed at the physician's discretion.

In the **second phase** of the study (Phase II), for those subjects who are randomized to **MPP ON**, the MPP feature will be programmed with mandated parameters as follows:

- MPP vector combination: Two programmable vectors with the widest spacing ([REDACTED]) between the two cathodes. The 'Widest Spacing' feature within the VectSelect Quartet™ MultiVector Tools in the Merlin Patient Care System should be used to program to widest spacing.
- LV1-LV2 delay: [REDACTED]
- LV2-RV delay: [REDACTED]

At 12 months, responder status will be assessed as follows:

- Subjects with LVESV reduction of at least 15% between Baseline and 12 months will be classified as responders.
- Subjects with LVESV reduction of less than 15% between Baseline and 12 months, or who died due to cardiac cause prior to the 12-month visit, will be classified as non-responders.

The percentage of non-responder subjects converted to responders after 6 months of MPP ON versus OFF will be assessed.

Statistical Analysis Plan**4.0 TRIAL ENDPOINTS****4.1 Primary Endpoint**

The primary endpoint of this study is evaluated at 12 months after implant (6 months after randomization) and is defined as the percentage of non-responder subjects converted to responders compared to baseline, as measured by LVESV reduction of at least 15%.

4.2 Secondary Endpoints

- Reduction of LVESV between baseline and 6 Months visit
- Packer’s Clinical Composite Score evaluation between baseline and 12 Months visit and between 6 Months and 12 Months visits
- Reverse LV remodeling, measured as changes in LVESV, [REDACTED] and LVEF
- NYHA Class changes
- 6 minutes walking test changes
- Quality of Life (MLWHF and EQ-5D) changes

5.0 STATISTICAL METHODS

This trial has one primary endpoint and 6 secondary endpoints.

5.1 Primary Endpoint Hypothesis

[REDACTED]

[REDACTED] ■ [REDACTED]

[REDACTED]

[REDACTED]

[REDACTED]

[REDACTED]

[REDACTED]

Study Document No: [REDACTED]

Study Name: MORE CRT MPP

Statistical Analysis Plan

5.1.1 Analysis Methods

The hypothesis will be tested at the one-sided 2.5% significance level. The null hypothesis will be rejected if the 97.5% lower confidence bound (LCB) for the difference between the proportion of subjects who are responders in the treatment group (MPP ON) and the proportion of subjects who are responders in the control group (MPP OFF), $(P_{ON}-P_{OFF})$, is greater than 0. The 97.5% LCB will be calculated using the Wald asymptotic confidence limits for difference of binomial proportions. [REDACTED]

5.1.2 Analysis Population

The primary endpoint analysis will be carried out on three subject cohorts:

- The **first subject cohort** (Cohort #1) [REDACTED]

- The **second subject cohort** (Cohort #2) [REDACTED]

- The **third subject cohort** (Cohort #3) [REDACTED]

Study Document No: [REDACTED]

Study Name: MORE CRT MPP

Statistical Analysis Plan

5.1.3 Sample Size

Phase I Sample Size

[REDACTED]

[REDACTED]

Phase II Sample Size

[REDACTED]

[REDACTED]

[REDACTED]

Statistical Analysis Plan**5.1.4 Sensitivity Analyses**

[REDACTED]

5.1.5 Timing of Analysis**Data Analysis of Phase I Subjects**

The analysis will be performed when all randomized non-responder subjects (confirmed by the Echo Core Lab) from Phase I study have either completed or crossed the 12-month visit window or discontinued before the 12-month visit. This analysis will be carried out on Cohort #1.

Data Analysis of Phase II Subjects

One interim analysis and a final analysis will be conducted.

- Interim Analysis

[REDACTED]

[REDACTED]

- The final analysis will be performed when all randomized non-responder Phase II subjects have either completed or crossed the 12-month visit window or discontinued before the 12-month visit.

Statistical Analysis Plan

- [REDACTED]
- [REDACTED]

5.1.6 Poolability Analysis

The poolability analysis between Cohort #2 and Cohort #3 subjects is planned at the interim and final analysis as follows:

[REDACTED]

[REDACTED]

[REDACTED]

[REDACTED]

[REDACTED]

[REDACTED]

Statistical Analysis Plan**5.1.7 Supplemental Analysis**

[REDACTED]

[REDACTED]

[REDACTED]

[REDACTED]

[REDACTED]

[REDACTED]

[REDACTED]

[REDACTED]

[REDACTED]

[REDACTED]

[REDACTED]

5.1.8 Subgroup Analyses

The following analyses of the primary endpoint may be performed for the following subgroups using the same datasets as those included in the primary endpoint analysis for publication purpose:

- [REDACTED]

[REDACTED]

Statistical Analysis Plan

[REDACTED]

[REDACTED]

[REDACTED]

[REDACTED]

[REDACTED]

[REDACTED]

[REDACTED]

5.2 Secondary Endpoints**5.2.1 Percent reduction (%) in LVESV from baseline to 6 months**

Percent reduction (%) in LVESV from baseline to 6 months will be summarized as sample size, mean, standard deviations, median and range. Subjects with missing LVESV at either Baseline or 6 months visit will be excluded from this analysis.

5.2.2 Packer’s Clinical Composite Score evaluation between baseline and 12 Months visit and between 6 months and 12 months visits.

Using the Packer’s clinical composite score (CCS), subjects are categorized as Improved, Worsened or Unchanged based on the following rules:

- “Worsened” – subjects that demonstrate:
 - Worsening in NYHA Class at last observation carried forward (LOCF) OR worsening by PGA (“worse” or “markedly worse”) at LOCF
OR
 - Presence of HF events as described in CIP
OR
 - Cardiac death
- “Improved” – subjects that demonstrate:

Study Document No: [REDACTED]

[figure not shown]
Study Name: MORE CRT MPP

Statistical Analysis Plan

- At least a one-class improvement in NYHA Class at LOCF OR improvement by PGA (“better” or “markedly better”) at LOCF
AND
- No HF events as described in CIP
AND
- No cardiac death

- “Unchanged” – subjects who have non-missing NYHA at LOCF or non-missing PGA at LOCF and are neither “Improved” nor “Worsened”.

If both NYHA and PGA are missing based on LOCF and doesn't have HF event and cardiac death, they will be excluded from the analysis.

Statistical Analysis Plan

Statistical Analysis Plan**5.2.3 Reverse LV remodeling, measured as % changes in LVESV, [REDACTED] and LVEF**

- [REDACTED]
- [REDACTED]

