[figure not shown]

[figure not shown]

[figure not shown]
Version 1.1, September 25, 2009

[figure not shown]

[figure not shown]

Part 2 - Packer's Clinical Composite Score (CCS)

The Packer's Clinical Composite Score (CCS) will be assessed at 6 months and 12 months post implant.

The CCS includes 4 components: NYHA class, Patient Global Assessment (PGA), HF events, and cardiovascular death²⁷.

The NYHA Class evaluation and PGA will be determined by an Investigator interviewing subjects about their symptoms. Specifically, the PGA will be a single interview question that asks the subject to categorize how they feel compared to their previous visits as either:

- Markedly better
- Better
- No change
- Worse
- Markedly worse

At the 6 Months Follow Up visit, a PGA will be conducted to evaluate how the subject feels compared to the baseline visit before having the CRT system implanted.

At the 12 Months Follow Up visit, two different PGAs will be conducted:

- The first one will evaluate how the subject feels compared to the baseline visit before having the CRT system implanted and
- The second one will evaluate how the subject feels compared to the 6-month visit.

In this trial a **HF event** is defined as any one of the following when the subject has symptoms and/or signs consistent with congestive heart failure:

- Hospitalization or Emergency Department visit for HF \geq 24 hours
- Hospitalization or Emergency Department visit for HF $<$ 24 hours requiring administration of IV inotropes or diuretics

Finally, **cardiovascular death** is defined as sudden unexpected death; heart failure death; myocardial infarction related; or 'other' such as pulmonary embolism, peripheral thromboembolism, stroke, deaths due to vascular procedure, or other major cardiovascular event.

Using the CCS decision algorithm described below, subjects are categorized as Improved, Worsened or Unchanged based on the following rules:

IMPROVED – subjects that demonstrate:

- At least a one-class improvement in NYHA Class OR improvement by PGA ("Better" or "Markedly better")
AND
- No HF events as described above
AND
- No Cardiovascular death

[figure not shown]
WORSENERD – subjects that demonstrate:

[figure not shown]
- Worsening in NYHA Class OR worsening by PGA ("Worse" or "Markedly worse")

[figure not shown]
- OR
- Presence of HF events as described above
- OR
- Cardiovascular death

[figure not shown]
UNCHANGED – subjects that are neither “Improved” nor “Worsened”.

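### On the clinical composite score, the visible text of SAP 5.2.2 counts cardiac death where the protocol counts cardiovascular death, and uses LOCF where protocol 7.6 bars imputation

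*Combined protocol and SAP*

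**What the plan says.** **Protocol.** Appendix E Part 2 sets out the score: "The CCS includes 4 components: NYHA class, Patient Global Assessment (PGA), HF events, and cardiovascular death". Its definition of cardiovascular death goes beyond the heart and takes in other causes "such as pulmonary embolism, peripheral thromboembolism, stroke, deaths due to vascular procedure, or other major cardiovascular event". The Improved rule requires "No Cardiovascular death", and the Worsened rule lists cardiovascular death as sufficient by itself. Section 4.2 (Patient Global Assessment) names the same death component. The symptom part of the Worsened rule reads "Worsening in NYHA Class OR worsening by PGA", with no reference to carried-forward values. Section 7.6 says in one unqualified sentence that no imputation will be used.

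**SAP 5.2.2.** The symptom part of the Worsened rule becomes "Worsening in NYHA Class at last observation carried forward (LOCF) OR worsening by PGA", and LOCF also appears in the Improved and Unchanged rules. The death term is cardiac death in the Worsened rule, "No cardiac death" in the Improved rule, and cardiac death again in the sentence on subjects with neither score, who are left out if they have no "HF event and cardiac death, they will be excluded from the analysis". For heart failure events the SAP refers back to the protocol ("Presence of HF events as described in CIP"). For death it gives no such reference.

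**The concern.** Two documents govern the same endpoint and can put the same patient in different categories. The death term matters more. A composite that counts cardiovascular death as worsening should not be able to score a fatal stroke as Improved, and the SAP's literal rules allow that. A programmer working from SAP 5.2.2 could also reuse the cardiac-death flag that the primary endpoint needs, since the primary endpoint does use cardiac cause (protocol 3.4 and 7.4, SAP 3.0).

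The LOCF conflict concerns whether a missing NYHA class or global assessment may be filled at all. If neither conflict is settled, the choice of rule can fall to whoever runs the analysis, possibly after the data are seen. The score is one of six secondary endpoints (SAP 5.0).

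**Working it through.** The plan states no figure on this point, so the check is a comparison of rules.

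**Step 1. Rules side by side**

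| Item | Protocol (Appendix E Part 2, 4.2, 7.6) | SAP 5.2.2 (visible text) |
|---|---|---|
| Death in Worsened rule | Cardiovascular, defined | Cardiac, not defined |
| Death in Improved rule | Cardiovascular | Cardiac |
| Death in exclusion sentence | No such sentence | Cardiac |
| NYHA and global assessment | LOCF not mentioned; 7.6 bars imputation | LOCF: Worsened 2 + Improved 2 + Unchanged 2 + exclusion 1 = 7 mentions |
| Unchanged | Anyone not Improved or Worsened | As protocol, but at least one score must be present after LOCF |
| Neither score, no HF event, no qualifying death | Falls into Unchanged if read literally | Excluded |

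**Step 2. One patient through both sets of rules.** Take a subject who dies of stroke between 6 and 12 months with no heart failure event. Under Appendix E the death alone makes the subject Worsened. Under SAP 5.2.2 a stroke death is not a cardiac death if the words are read literally, and there is no 12-month visit to observe. The category then depends on what LOCF supplies: a carried value showing improvement gives Improved, one showing no change gives Unchanged, and no value at all gives exclusion. A carried value showing deterioration would still give Worsened, so the documents differ for some of these subjects, not necessarily all.

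**Step 3. What LOCF could carry.** Protocol Table 2 schedules the global assessment at 6 and 12 months only, and NYHA class at baseline, 6 and 12 months. Randomisation is at the 6-month visit. The last scheduled value before 12 months is therefore the one taken at the randomisation visit. If such values may not be carried, only values from unscheduled visits remain. If they may, a 6-month NYHA class carried into the 6-to-12-month comparison gives no change by construction, and the 6-month global assessment refers to baseline, not to the 6-month visit. The visible SAP text does not say which applies.

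**Step 4. Size of the death-term effect, by assumption only.** The documents give no rate of non-cardiac cardiovascular death. Assume an arm of 500 and 0.2% to 1% of it dying this way without a heart failure event:

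- Subjects affected: 0.002 × 500 = 1, up to 0.01 × 500 = 5.
- Largest fall in that arm's Worsened share: 1/500 = 0.2 points, up to 5/500 = 1.0 point.
- Example with an assumed 30% Worsened under the protocol: 150/500 = 30.0%. Five deaths scored Improved or Unchanged give 145/500 = 29.0%; five deaths excluded give 145/495 = 29.3%.
- Between arms: about 0 if the rates are equal and the deaths are handled alike; 1.0 − 0.2 = 0.8 points if the rates are 1% and 0.2% and all these deaths are scored Improved or Unchanged. Each arm's share can only fall, by at most 1.0 point, so the difference cannot move by more than 1.0 point under these assumptions.

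No size is offered for LOCF, because the documents give no rate of missing NYHA class or global assessment.

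**The case against.** **Cardiac may be loose wording for cardiovascular.** SAP 5.2.2 presents its rules as Packer's score, whose death component the protocol defines, and the SAP nowhere contrasts the two terms in visible text. This remains possible. Against it, SAP 6.2 uses cardiovascular mortality, the protocol uses cardiac death for the primary endpoint and cardiovascular death for this score, and 5.2.2 imports the protocol definition for heart failure events only. Even if the wording is loose, it needs correcting.

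**Section 7 leaves secondary-endpoint analysis to the SAP.** It does, as additional detail. That may explain the mismatch, but replacing a component or reversing a missing-data rule is not added detail, and 7.6 makes no exception for secondary endpoints. What stands is that the LOCF item is a question of consistency. It does not show that LOCF is the wrong analysis.

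**Much of the relevant text cannot be seen.** The SAP contents list places 5.2.2 on pages 12 to 15, and about a page of it is not shown. The protocol's decision-algorithm figure is also not shown, and the revision rationale in SAP 7.2 is redacted. A definition, an LOCF window or a reason for the change could be there. This stands in full and limits confidence about what would happen to actual patients.

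**A stronger reading to resist.** A reader might infer from Step 3 that the SAP carries pre-randomisation scores to 12 months and so pulls the arms together. The documents do not support that claim: the visible text neither permits nor forbids it. The absence of an LOCF window cannot be claimed either.

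**Conclusion.** The death term in SAP 5.2.2 is wrong as written against the protocol and should be fixed. The LOCF conflict with 7.6 is a smaller consistency point. Confidence is high that the visible wording conflicts, and moderate that patients would be classified differently.

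The effect cannot be computed from the documents. It is likely small: under the assumed rates of 0.2% to 1%, the death term moves one arm's Worsened share by at most 1.0 point. A reader might infer that the trial's main result is at risk. It is not: the primary endpoint rests on LVESV with its own cardiac-cause rule, and SAP 6.2 reports all-cause and cardiovascular mortality separately. The trial success section is redacted, so nothing visible shows a decision resting on this score.

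**What to change.** 1. **Death term.** In the Worsened rule, the Improved rule and the exclusion sentence of SAP 5.2.2, replace cardiac death with *cardiovascular death as described in CIP*, the form of reference already used there for heart failure events. Leave the primary endpoint's cardiac-cause rule as it is.
2. **LOCF.** Remove it from SAP 5.2.2 and score on NYHA class and global assessment observed at the visit. Keep the SAP's requirement of at least one non-missing score for Unchanged.
3. **Appendix E.** Align its Unchanged rule with that requirement. Otherwise a subject with no score still falls into Unchanged under the protocol and is excluded under the SAP.
4. **If the sponsor prefers LOCF,** write an explicit exception into protocol 7.6 and state which visits may be carried. If pre-randomisation values are barred, only unscheduled-visit values are left, so little would remain of the method.

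**Cost.** Three wording changes and the LOCF deletions in the SAP, a one-line change to Appendix E (or, with LOCF kept, a sentence in 7.6), and matching derivation code. No new data are needed. The downside of removing LOCF is that subjects with neither score, no heart failure event and no cardiovascular death are not scored; their number should be reported by arm.

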The Patient Global Assessment will be performed at 6 and 12 Months Follow Up visits and will be used to calculate the Packer's Clinical Composite Score (CCS) together with NYHA Class evaluation, HF events and/or Cardiovascular death.

For further information regarding CCS please refer to Appendix E "Guidelines" part 2.

NYHA Class evaluation:

The subject's New York Heart Association class will be assessed at Baseline and during all Follow-up Visits.

Randomization procedure (only for Non Responders to CRT):

The randomization procedure will be performed at 6 Months Follow Up only for subjects that are classified as NON RESPONDERS to CRT. The randomization will be stratified by center and will assign the subjects either to MPP ON or MPP OFF in a 1:1 fashion.

12-Lead ECG (EDC upload):

A 12-lead ECG must be performed at Baseline, 6 and 12 Months Follow-up Visit.

The anonymized 12-Lead ECG (performed at paper speed 25mm/s or 50mm/s depending on center's preference) should be uploaded to the Electronic data Capture (EDC) system using the feature "Attachments to CRFs", for further details on this topic please refer to Appendix E "Guidelines" part 1.1.

The following data will be retrieved:

- Date of ECG
- Heart rate
- Atrial and Ventricular rhythms
- QRS width
- PR Interval
- LBBB or RBBB occurrences

B-Type natriuretic peptide (BNP), pro-BNP or NT-pro-BNP test (if performed per Standard of Care):

The BNP/pro-BNP/NT-pro-BNP test is used to measure the amount of stress on the subject's heart. If this test will be performed as per Standard of Care in the participating centers, the result will be collected at Baseline, 6 and 12 months follow-up. The test kit established at the investigational site will be used and intra-individual changes from Baseline to FU will be calculated.

6 Minute Hall Walk test:

The 6 Minute Hall Walk test is used to measure the subject's health status and must be completed at Baseline, 6 Months and 12 Months Follow Ups. The 6 Minute Hall Walk test measures the distance an individual is able to walk over a total of six minutes on a hard, flat surface. The goal is for the individual to walk as far as possible in six minutes. The individual is allowed to self-pace, rest as needed or interrupt the test at any time.

EQ-5D Questionnaire:

In order to assess the subject's health status, an EQ-5D questionnaire must be completed at Baseline, 6 Months and 12 Months Follow Ups.

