- If the subject is evaluated as a Responder by the center and as a Non Responder by the Core Lab: the center should call back the subject for the randomization procedure (within a reasonable time window (e.g. 2 weeks) after the 6M visit).

Conduction Delays Test:

The conduction delays between right and left ventricle will be performed during implant and each in-clinic follow up. This is an automatic test that can be performed via Merlin PCS programmer and will end in about one minute. Please refer to Appendix E: “Guidelines” part 3 for further details regarding the Conduction Delay test.

Device Test and Programming (EDC upload):

Device will be interrogated and all the diagnostics retrieved; standard sensing, pacing and impedance measurements will be performed for all implanted leads at each in-clinic follow-up. Please refer to Appendix E “Guidelines” part 1.2 for further details on the “Upload Device Data” procedure.

The device programming will be left to Investigator's discretion with the exception of the MPP feature. It is suggested that AV delay optimization is performed per centers' preference.

Please see below the MPP Programming activity.

Follow-up session (including diagnostics) will be uploaded to the EDC system using the feature "Upload Device Data".

MPP Programming:

Overall device programming will be left to the Investigator's discretion with the exception of the MPP feature:

- **MPP should NOT be programmed ON BEFORE** the 6 Months FU
- At the 6 Months FU, the MPP feature will be programmed ON or OFF as per Randomization result (1:1) for subjects classified as NON RESPONDERS according to LVESV reduction less than 15%. Subjects randomized to MPP ON in the second phase of the study should be programmed as follows:
 - MPP Vector combination: Two programmable vectors with widest spacing (≥ 30 mm between two cathodes). The 'Widest Spacing' feature within the VectSelect Quartet™ MultiVector Tools in the Merlin Patient Care System should be used to program to widest spacing.
 - LV1-LV2 delay: 5 ms
 - LV2-RV delay: 5 ms

Please refer to Appendix E: "Guidelines" Part 2 for further details regarding subject's CRT response classification and Part 7 for further details about MPP Programming.

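### As readable, SAP 5.2.2 lets Month 6 NYHA and PGA, taken before MPP may be switched on, stand in for a missing 12-month clinical composite assessment

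*Combined protocol and SAP*

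**What the plan says.** SAP 5.2.2 covers Packer's Clinical Composite Score "evaluation between baseline and 12 Months visit and between 6 months and 12 months visits". It sorts subjects into *Worsened*, *Improved* or *Unchanged*, and both symptom components are taken by last observation carried forward. The first criterion for *Worsened* begins "Worsening in NYHA Class at last observation carried forward (LOCF" and gives worsening on the PGA, also carried forward, as the alternative; *Improved* and *Unchanged* use the same device. An HF event or a cardiac death gives *Worsened* whatever NYHA and PGA show. The exclusion sentence opens "If both NYHA and PGA are missing based on LOCF" and applies only when there is also no HF event and no cardiac death.

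The protocol fixes what there is to carry:

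- **PGA** (section 4.2): "The Patient Global Assessment will be performed at 6 and 12 Months Follow Up visits".
- **NYHA** (section 4.2): the "class will be assessed at Baseline and during all Follow-up Visits". Table 2 makes NYHA mandatory at Baseline, Month 6 and Month 12.
- **MPP** (section 4.2, MPP Programming): "MPP should NOT be programmed ON BEFORE" the 6-month follow-up. Non-responders are randomised at that visit.
- **PGA reference point** (Appendix E, Part 2): the Month 6 question asks about change since baseline. Two questions are put at Month 12, one against baseline and one against Month 6: "The second one will evaluate how the subject feels compared to the 6-month visit".
- **Unscheduled visits** (section 4.2.7): changes in NYHA are recorded where applicable. PGA is not listed.
- **Missing data** (section 7.6): imputation is ruled out.

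**The concern.** Carrying an observation forward makes sense when the carried value was taken during the treatment period being judged. Here the schedule has no NYHA or PGA between randomisation and Month 12. For a subject who misses Month 12, the last observation will normally be the Month 6 one, made under standard CRT with MPP off in both arms. The table would then report run-in status as a 12-month outcome.

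What is at stake is the arm comparison for a listed secondary endpoint that speaks directly to the secondary objective, functional and clinical status. If absence is equal, the comparison is pulled towards no difference. If subjects leave because they are deteriorating, and more do so in one arm, they keep their earlier label and the comparison may be biased.

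**Working it through.** The readable documents give no sample size, power or rate for the composite, so there is no planned figure to reproduce. The check has two parts: apply the rule to one subject, then illustrate its size under stated assumptions.

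**Step 1. The subject.** Randomised at Month 6; no Month 12 NYHA or PGA; no HF event; no cardiac death; no NYHA from an unscheduled visit. The latest values available are NYHA and PGA from Month 6. Baseline NYHA also exists, but it is older and also precedes randomisation.

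**Step 2. Apply SAP 5.2.2.**

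| Window | NYHA | PGA | Score |
|---|---|---|---|
| Baseline to 12 months | Month 6 against baseline | Month 6 answer, about change since baseline | The baseline-to-6-month score |
| 6 to 12 months, PGA carried question by question | Month 6 against Month 6, change = 0 | Change-since-Month-6 question never asked, so missing | *Unchanged* |
| 6 to 12 months, Month 6 PGA carried | Change = 0 | Answer about change since baseline | Better or markedly better gives *Improved*; no change gives *Unchanged*; worse or markedly worse gives *Worsened* |

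No row contains post-randomisation information. In the first row the PGA reference point is right but the score is the run-in result. In the third, the subject's view of six months on standard CRT is scored as the result of the randomised period.

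**Step 3. The exclusion sentence.** It needs both NYHA and PGA to be missing after carrying forward. Both are mandatory at Month 6, so if Month 6 values are eligible it almost never applies.

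**Step 4. Equal absence (illustration).** Assume a share m of each arm is scored on Month 6 data with the same expected distribution in both arms, and a true difference D among those assessed. The expected observed difference is (1 − m) × D. With D = 10 points:

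- m = 5%: 0.95 × 10 = 9.5 points
- m = 10%: 0.90 × 10 = 9.0 points
- m = 15%: 0.85 × 10 = 8.5 points

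For a comparison sized at 80% power, two-sided 5% (376 per arm for 35% against 45%, or 392 for 45% against 55%), with 50% of carried scores *Improved*, power falls to about 76%, 71% and 66%. These are not the trial's own sample sizes.

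**Step 5. Unequal absence, no true effect (illustration).** Assume 60% of carried and 40% of observed scores are *Improved*, with 15% absent on MPP ON and 5% on MPP OFF.

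- ON: 0.85 × 40% + 0.15 × 60% = 43%
- OFF: 0.95 × 40% + 0.05 × 60% = 41%
- Spurious difference: 43% − 41% = 2 points. Reversing the absence rates reverses the sign.

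**Step 6. A ceiling.** If 12% of one arm and 6% of the other left because they were worse, up to 12% − 6% = 6 points of difference in *Worsened* would go uncounted. That maximum needs every leaver to have deteriorated, none to have had a recorded HF event or cardiac death, and none to have been *Worsened* already at Month 6.

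**The case against.** **Part of the section cannot be read.** The SAP contents list puts 5.2.2 on page 12 and 5.2.3 on page 15, while the readable text fills about two pages. A limit on eligible visits could sit on the page that appears unreadable, or in a figure that is not shown. This stands: the point can only be made about the rule as readable.

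**The exclusion sentence may imply a limit.** If only post-randomisation values were eligible, that sentence would have a real purpose, and an unscheduled visit can supply a NYHA. The reading is possible, but the readable text does not state it.

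**The PGA substitution is not written down.** A reader might infer that the SAP scores the 6-to-12-month window on the wrong PGA question. The documents do not establish that: the question about change since Month 6 is first asked at Month 12, so question-by-question carrying leaves it missing. The subject is then *Unchanged*, because Month 6 NYHA is compared with itself. That score still reflects nothing after randomisation, so the defect survives on either reading.

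**Protocol 7.6 may settle it.** If its bar on imputation governs the composite, carrying forward goes and so does this point. If the conflict is settled in favour of carrying forward, the defect remains.

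**Exclusion is no cure for informative drop-out.** Correct. Dropping these subjects gives a complete-case analysis, in which deteriorating leavers remain uncounted. That is why the fix needs more than the exclusion.

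**Conclusion.** Wrong as written, on the readable text. SAP 5.2.2 does not stop pre-randomisation NYHA and PGA from deciding a 12-month composite score, and the visit schedule makes that the usual result for the subject in Step 1. Not every absent subject is affected: those with an HF event or cardiac death score *Worsened* regardless, and an unscheduled NYHA may supply a later value.

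The expected effect is dilution in proportion to absence when absence is equal between arms, and possible bias when it is not. The absence rates, the 10-point difference and the composite rates are all assumptions. A reader might take the 6-point figure as an estimate of hidden worsening; it is only an upper limit under extreme conditions. The point concerns one of six secondary endpoints. The primary LVESV endpoint is unaffected.

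**What to change.** 1. In SAP 5.2.2, allow carrying forward only of NYHA or PGA recorded after randomisation, and of PGA only when it answers the comparison being scored (against baseline or against Month 6).
2. Treat a subject with no post-randomisation NYHA or PGA, no HF event and no cardiac death as missing under the existing exclusion sentence.
3. Report the number so excluded in each arm, and add one sensitivity table that counts them as *Worsened*. This is a deliberately severe convention, meant to show how far informative drop-out could move the result.
4. Reconcile the rule with protocol section 7.6, so that the two documents agree on whether any carrying forward is allowed for this endpoint.

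If the unreadable part of 5.2.2 already limits the eligible visits and the PGA question, items 1 and 2 need only be confirmed.

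The cost is SAP wording, one extra table and slightly fewer scored subjects in the main table. No new data are needed.
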